2.0 Objectives*

2.1 Describe the purpose, **specific aims**, or objectives.

Purpose: The purpose of this research is to develop a midlife **B**lack women's **Stress**-reduction **WELL**ness intervention, **B-SWELL**, to promote healthy lifestyle behaviors based on the stressors and themes identified in the PI's preliminary research and consistent with the American Heart Association's *Life Simple 7 Success Plan (LS7) behaviors*.

Aim 1: Develop the B-SWELL intervention for midlife Black women through the innovative leveraging of CBPR methodology and LS7 modifiable healthy lifestyle behaviors.

- a) To develop components of the B-SWELL intervention prototype for midlife Black women.
- b) Obtain ratings of the new components of the B-SWELL from an expert panel consisting of four midlife Black women laypersons, three researchers and three integrative health care specialists for degree of accuracy, relevance, and feasibility to inform further refinements.

Aim 2: Determine the feasibility of the B-SWELL intervention with a trial of 50 midlife Black women randomized to the B-SWELL intervention (25) or to a wellness education (WE) control group (25):

- a) Obtain recruitment, retention, treatment fidelity ratings, and satisfaction ratings for the intervention procedures for both groups, including technology;
- b) Compare mediator measures (stress, self-efficacy) for participants in the B-SWELL intervention group with those in the WE group at 8 and 12 weeks.
- c) Compare outcome measures (LS7 summary scores, unhealthy days, general health, depressive symptoms) for participants in the B-SWELL intervention group with those in the WE attention control group at 8 and 12 weeks.
- 2.2 State the hypotheses to be tested.

Our hypothesis proposes that B-SWELL (intervention) participants will show improved self-efficacy in managing life stress and adopting the LS7 behaviors, compared to an attention control group (WE group) receiving traditional wellness education.

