17.0 Data Management* and Confidentiality

17.1 Describe the data analysis plan, including any statistical procedures or power analysis.

In Aim 1 and Aim 2a, numerical measures will be summarized using descriptive statistics (i.e., means, standard deviations, and frequencies) regarding expert ratings of degrees of accuracy, relevance and feasibility of new components of the B-SWELL program (Aim 1), and recruitment, retention, treatment fidelity ratings, and satisfaction ratings (Aim 2a). For Aims 2b and 2c, numerical dependent variables (stress, self-efficacy, LS7 scores, unhealthy days, perceived general health, depressive symptoms) will be inspected of empirical distributions to ensure they meet conditions for parametric statistical models. Variable transformation will be used otherwise. All statistical tests will be performed using SPSS Version 25. Parameter estimates with P-values less than .05 will be considered statistically significant. Assumptions related to each statistical test used will be checked using residual plots, qq-plots, and tests for homogeneity of variance/ covariance. In Aim 2b, continuous mediators (stress, self-efficacy) will be compared between groups (B-SWELL vs WE) using t-tests at each visit (baseline, 8 weeks, 12 weeks).

In Aim 2c, using mixed effect models, primary (i.e., LS7 summary scores) and secondary outcome measures (i.e., unhealthy days, perceived general health, depressive symptoms) will be assessed for their associations with time (baseline, 8 weeks, 12 weeks), group (B-SWELL vs. WE), and interaction. In particular, each of the outcome measures will be treated as the dependent variable, and the time effect, group effect, and the interaction will be treated as independent variables or fixed effects of interest in the mixed effect model. Random effects will be used to account for within person correlation due to repeated measurements. Other covariates, such as demographics and attendance rate, will be controlled for by including them in the model and checking for their interaction with the intervention. Post hoc analysis of group means will be compared cross-sectionally, as well as longitudinally between time points (such as week 8 or 12 vs. baseline). Considering the limited sample size for this pilot-type of study, statistical tests will not be adjusted for multiple comparisons in post hoc analyses. Significant findings will be considered preliminary in nature and inspire future research.

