Power. Statistical power is analyzed based upon assumptions that we have N=50 total or N=25/group complete all four data collection time points with complete observations. Should there be any concern of dropout from the study, we will over sample participants at baseline to offset the predicted dropout rate and ensure the proposed sample size in the final visit. The statistical tests are two sided with a targeted significance level of 0.05. In Aim2b and Aim2c post hoc analyses when we compare means using a two group t-test with equal variances assumption, we will reach 85% power to detect an effect size (i.e. difference of means/standard deviation of the difference) of 0.87.73 In Aim2c when we compare means using a paired t-test between visits in a group, we will reach the 85% power to detect an effect size of 0.63.73 If possible, and plausible, missing data could be included into analysis after multiple imputation, thus increasing the sample size and statistical power to detect differences. The main emphasis will be on exploring data trends to inform future work, rather than

significance, since this is a feasibility study. Significance will be emphasized when testing efficacy of the B-SWELL intervention compared to the WE attention control group in a future, well-powered RCT.

17.2 Describe the steps that will be taken to secure the data during storage, use, and transmission.

All study data and tracking will be entered into an electronic data system, REDCap (www.REDCap.org), a secure research electronic data management system with validated data entry, audit trails for tracking data manipulation, and export procedures. It is HIPAA complaint satisfying all local, state, and federal regulation for the capture and storage of private health information for research purposes. The PI is familiar with RedCap through prior research projects. The PI is committed to compliance with HIPAA, data safety procedures, NIH recommendations, and CITI trainings. All research personnel will be trained in the use of secure data and RedCap prior to their participation in the study and any communication with participants.

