19.0 Provisions to Protect the Privacy Interests of Subjects

19.1 Describe the steps that will be taken to protect subjects' privacy interests.

Participants may choose not to answer items during interviews or participate in portions of the intervention program with which they are uncomfortable. Participants will be informed that participation in the study is voluntary and that they are free to discontinue participation at any time. Participants will be informed of risks related to privacy using an online format (Zoom).

19.2 Describe what steps you will take to make the subjects feel at ease with the research situation in terms of the questions being asked and the procedures being performed

Recruitment and retention of Black women in research studies is a historic problem. Using communitybased participatory research (CBPR) methods, our team hopes to achieve optimal recruitment numbers and minimize attrition in this study. CBPR techniques, such as community engagement, will assist in targeting and tailoring the study procedures, thereby increasing its appeal to a large number of midlife Black women in the Greater Cincinnati area. Collaboration with an experienced community research advisory board will guide the recruitment efforts and selection of study sites. Recruitment activities will include the use of fliers and pamphlets, referral, snow balling, and/or remote community presentations. All potential participants will be provided with written information about the nature, purpose, and possible risks and benefits of the study.

Transparency and full disclosure are necessary to improve retention. Participants will be informed that participation in the study is voluntary and that they are free to discontinue participation at any time. Research staff having contact with the participants in the study will be trained using this process in the event that at any time the participant has any questions or wishes to withdraw. To prevent attrition, duplicates will be built into the program when possible to accommodate participant's schedules. Group session times will be selected based on availability of participants. In addition, phone or text messages will be sent to remind participants about the sessions and incentives will be offered after each of the four data collection time-points.

19.3 Indicate how the research team is permitted to access any sources of information about the subjects.

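### Aim 2c fits a mixed model, but the only test named for its between-group post hoc comparisons is a two-group t-test, which is biased at 8 and 12 weeks if dropout depends on earlier scores differently in the two arms

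*Combined protocol and SAP*

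**What the plan says.** Aim 2c (section 2.1) is a between-group aim at two named visits, 8 and 12 weeks: "Compare outcome measures (LS7 summary scores, unhealthy days, general health, depressive symptoms) for participants in the B-SWELL intervention group", set against the WE group.

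Section 17.1 gives the main analysis as a mixed model in which "the time effect, group effect, and the interaction will be treated as independent variables or fixed effects of interest in the mixed effect model", with random effects for repeated measurements. Demographics and attendance rate are to be added as covariates. It continues: "Post hoc analysis of group means will be compared cross-sectionally, as well as longitudinally between time points".

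The power paragraph of the same section names tests for these comparisons. Between groups: "In Aim2b and Aim2c post hoc analyses when we compare means using a two group t-test with equal variances assumption". Within a group: "In Aim2c when we compare means using a paired t-test between visits in a group, we will reach the 85% power to detect"; the standardised difference given there is 0.63. The calculation assumes "N=50 total or N=25/group complete all four data collection time points with complete observations". (The count of four does not match the three visits scheduled elsewhere; this point does not depend on it.)

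On missing data, section 17.1 plans oversampling at baseline and allows multiple imputation where possible and plausible, without an imputation model or a rule for when it applies. Under section 14.3, data collection stops when a woman withdraws. Section 19.2 acknowledges that "Recruitment and retention of Black women in research studies is a historic problem".

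**The concern.** A likelihood-based repeated-measures model uses every observed visit. If its mean and covariance structure are right, its visit-specific contrasts stay valid when dropout depends on scores already observed. A t-test at week 12 without imputation uses only the women present at week 12 and ignores what is known about those who left.

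The plan therefore fits a method that can handle this kind of dropout, yet the wording attaches the comparisons Aim 2c asks for to one that cannot. Oversampling restores numbers but does not undo selection. The reason given for imputation is sample size and power, not bias.

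Dropout that differs by arm is conceivable here. The arms receive different content, and participants are told their assignment (section 6.2.2). The study is meant to support a larger trial (section 6.1), so a distorted effect estimate could be carried into its planning.

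**Working it through.** **1. The plan's own figures.** Inputs from section 17.1: 25 per group, effect sizes 0.87 and 0.63, 85% power, and "The statistical tests are two sided with a targeted significance level of 0.05". Power is taken from the noncentral t distribution.

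- Two-group: noncentrality 0.87/√(2/25) = 3.076, 48 df, critical value 2.011, power 0.854.
- Paired: noncentrality 0.63 × √25 = 3.15, 24 df, critical value 2.064, power 0.856.

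Both reproduce the stated 85%. The planning calculation is thus for t-tests on 25 complete cases per group.

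**2. When is a week-12 t-test biased?** The following are assumptions, because the documents give none: unit SD; correlations 0.5 (baseline to week 8), 0.45 (baseline to week 12) and 0.7 (week 8 to week 12); about 18% missing at week 12 in each arm; no true effect.

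Let X be the week-8 score and Y the week-12 score. If staying depends only on X, the mean of Y among stayers is 0.7 × E[X | stays]. The false difference is the gap between the arms in this quantity.

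- *Same rule in both arms:* the two terms are equal and the difference is 0.
- *Mild, one arm:* the log-odds of dropout rise by 0.5 per SD of X, with random 18% loss in the other arm. E[X·p(X)] = 0.5 × E[p(1−p)] ≈ 0.5 × 0.142 = 0.071. Then 0.071/0.82 = 0.087, and 0.7 × 0.087 ≈ 0.06 SD.
- *Severe, one arm:* 60% of women with X above 0.5 are lost, with random 18% loss in the other arm. P(X > 0.5) = 0.3085, so 0.6 × 0.3085 = 18.5% are lost. E[X | stays] = −0.6 × 0.3521/0.815 = −0.259, and 0.7 × 0.259 ≈ 0.18 SD. That is 0.18/0.87 = 21% of the effect size in the power statement.

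Simulation at 25 per arm agrees:

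| Dependence of dropout on week-8 score | False week-12 difference, t-test | Rejection at 5% | Bias, likelihood estimate using baseline and week 8 |
|---|---|---|---|
| Same in both arms | about 0.00 SD | about 5% | about 0.00 |
| Mild, one arm | about 0.06 SD | 5.5–5.8% | about 0.00 |
| Severe, one arm | about 0.18 SD | 8.6–8.9% | about 0.00 |

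**3. A second set of assumptions.** Here dropout occurs in both intervals at 10% for a woman at the mean score. Its odds change e-fold per SD of the previous score, correlations are all 0.5 or all 0.7, and 19–24% are missing at week 12. With no true effect, the week-12 difference in observed means is about 0 (same dependence in both arms), 0.12–0.16 SD (one arm) or 0.22–0.31 SD (opposite directions). At week 8 the last two are about 0.05–0.08 and 0.12–0.16 SD. With a true difference of 0.50 SD, same-direction dependence gives 0.48–0.49. A repeated-measures model with unstructured covariance recovers 0.49–0.51 throughout.

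**4. Does any mixed model do?** No. In the severe scenario of step 2, a random-intercept-only model leaves about 0.04 SD of bias, because it forces the three between-visit correlations to be equal. Unstructured covariance leaves about 0.00.

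**5. Precision.** In the step 3 simulations at 25 per arm, the standard error at week 12 is about 0.30–0.31 SD for the model and 0.31–0.32 SD for the t-test. The gain is in bias, not precision.

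**The case against.** **The t-test wording sits in the power paragraph.** The analysis text names t-tests only for Aim 2b. Its sentence on Aim 2c post hoc means follows the mixed model directly and is compatible with model-based means. A reader might infer that the plan has settled on completer t-tests for Aim 2c. The documents do not go that far: no section restricts the comparison to women present at the visit, and imputation is permitted. What remains is that the t-test is the only test named for these comparisons, and no section calls them model contrasts.

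**The group-by-time interaction already compares the arms using all observed data.** True. However, its overall test across three visits does not estimate the difference at week 8 or week 12.

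**Dropout related to earlier scores is not enough.** This stands. A reader might infer that any such dropout biases the t-test, but with the same dependence in both arms the bias is at most about 0.02 SD. Section 19.2 describes a general retention problem and introduces measures against it. It is not evidence that dropout will differ by arm.

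**The model as written is not a clean remedy.** This also stands. Section 17.1 would adjust for attendance rate, which is measured after randomisation, so the contrast would be conditional on attendance. It also leaves the random-effects structure open.

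**This is a pilot.** Findings are labelled preliminary, efficacy is deferred to a later trial, and no decision rule rests on a week-12 test. That limits the consequence to the effect estimates.

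**Conclusion.** The point holds in a conditional form. The plan fits a mixed model for Aim 2c but names only a two-group equal-variance t-test for the between-group follow-up comparisons. Without imputation, that test is open to selection through dropout.

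The bias is material only if dropout depends on earlier scores differently in the two arms. Under the step 2 assumptions the false week-12 difference runs from about 0, through 0.06 SD, to 0.18 SD with about 9% rejection. The second set of assumptions reaches 0.31 SD, when the dependence runs in opposite directions. Dropout rate, mechanism and correlations are all assumed, so these figures show what could happen and do not forecast this trial. The model's protection in turn assumes that dropout depends only on observed data.

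The feasibility results are not threatened. Because the correction is almost free and the effect estimates are meant to inform a larger trial, the change is worth making.

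**What to change.** In the analysis text of section 17.1, state that:

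- the Aim 2c group differences at 8 and 12 weeks are estimated marginal mean contrasts, with 95% confidence intervals, from the group-by-visit mixed model;
- the covariance across the three visits is unstructured, with a simpler structure only if that fails to converge;
- every randomised woman with any observation is included;
- attendance rate and other post-randomisation variables are left out of the model that yields these contrasts;
- the two-group t-tests are kept as a completer sensitivity analysis.

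If model contrasts were always intended, the first item is a clarification. The cost is a few sentences and contrast statements in a model already planned. No new data or additional participants are needed.

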18.0 Provisions to Monitor the Data to Ensure the Safety of Subjects*

This section is required when research involves more than Minimal Risk to subjects.

N/A

19.0 Provisions to Protect the Privacy Interests of Subjects

19.1 Describe the steps that will be taken to protect subjects' privacy interests.

Participants may choose not to answer items during interviews or participate in portions of the intervention program with which they are uncomfortable. Participants will be informed that participation in the study is voluntary and that they are free to discontinue participation at any time. Participants will be informed of risks related to privacy using an online format (Zoom).

19.2 Describe what steps you will take to make the subjects feel at ease with the research situation in terms of the questions being asked and the procedures being performed

Recruitment and retention of Black women in research studies is a historic problem. Using communitybased participatory research (CBPR) methods, our team hopes to achieve optimal recruitment numbers and minimize attrition in this study. CBPR techniques, such as community engagement, will assist in targeting and tailoring the study procedures, thereby increasing its appeal to a large number of midlife Black women in the Greater Cincinnati area. Collaboration with an experienced community research advisory board will guide the recruitment efforts and selection of study sites. Recruitment activities will include the use of fliers and pamphlets, referral, snow balling, and/or remote community presentations. All potential participants will be provided with written information about the nature, purpose, and possible risks and benefits of the study.

Transparency and full disclosure are necessary to improve retention. Participants will be informed that participation in the study is voluntary and that they are free to discontinue participation at any time. Research staff having contact with the participants in the study will be trained using this process in the event that at any time the participant has any questions or wishes to withdraw. To prevent attrition, duplicates will be built into the program when possible to accommodate participant's schedules. Group session times will be selected based on availability of participants. In addition, phone or text messages will be sent to remind participants about the sessions and incentives will be offered after each of the four data collection time-points.

19.3 Indicate how the research team is permitted to access any sources of information about the subjects.

Participants may choose not to answer items during interviews or participate in portions of the intervention program with which they are uncomfortable.

Only authorized study personnel will have access to the database or contact information for study participants and expert panel members. For data analysis, study ID numbers will be generated to protect the identity of the participants in the final data set. Participants will not be identified in any way in reports or manuscripts from the study. Data from surveys will input directly into a REDCap database. REDCap is backed up nightly by the university. Only authorized study personnel will have access to REDCap. All calls to participants will be made to a telephone number provided by the participant at a time that is convenient for the participant. Research staff will make calls from a private location in order to protect confidentiality. Informed consent forms and contact information from participants will be stored separately in a locked file cabinet to protect confidentiality.

20.0 Compensation for Research-Related Injury

N/A

21.0 Economic Burden to Subjects

21.1 Describe any costs that subjects may be responsible for because of participation in the research.

There is no cost to participate in this study.

22.0 Consent Process

22.1 Indicate whether you will you be obtaining consent, and if so describe:

For Aim 1, experts will receive a study information sheet explaining that participation is voluntary and that their decision will not affect their relationship with the University of Cincinnati, their employer, or the researchers. Full information will be provided and questions answered prior to consent. Consent will be obtained prior to the start of the study.

For Aim 2, participants will receive full information about the nature, purpose, and possible risks and benefits of the study. Participants will be informed that participation in the study is voluntary, and they are free to discontinue participation at any time. Those who are eligible and who have signed the informed consent will be enrolled. Eligibility will be determined via phone. Participants will receive an information sheet for their records following screening, receipt of study details, a question/answer period, and verbal consent. Consent will take place prior to collection of baseline data. There may be a brief waiting period between notification of eligibility and consent.

We will be following "SOP: Informed Consent Process for Research.

Ongoing consent is not required. We are seeking consent for participation in the study for a duration of 12 weeks.

Non-English Speaking Subjects

N/A

Waiver or Alteration of Consent Process (consent will not be obtained, required information will not be disclosed, or the research involves deception)

N/A

Subjects who are not yet adults (infants, children, teenagers)

N/A

Cognitively Impaired Adults

N/A

Adults Unable to Consent

N/A

Adults Unable to Consent

N/A

